7.7.1 Breaking Randomization

Randomization may be broken and the patient taken off protocol for any of the following reasons. In all cases the new threshold will be noted and the patient will be observed for primary and secondary outcomes until the completion of the study period.

Randomization will be immediately broken and transfusions managed according to the subject's managing provider(s) for any grade 3 or 4 bleeding event. The new threshold will be noted and the patient will be followed for outcomes until the end of the study period. If a grade 3 event completely resolves in <72 hours, is non-life-threatening, does not require permanent discontinuation of anticoagulation and is not reasonably expected to recur (eg vaginal bleeding resolved with hormonal therapy, bleeding from a wound which has been closed), the patient and primary provider may elect to continue with the randomized threshold.

For subjects in whom discontinuation of anticoagulation is deemed necessary by managing providers, randomization will be broken, and a new transfusion threshold will be determined at the discretion of the managing team.

7.8 Duration of Follow-Up

Follow-up after completion of the study period will involve a single, in-person or telephone visit which will occur 30 +/- 5 days after the end of the study period. The visit will include chart review, verbal history and, if appropriate, a brief physical exam for evidence of bleeding or thrombosis.

8.0 Subject Evaluation

8.1 Primary Endpoint

As this is a feasibility study, the primary goal is to determine the number of centers and duration of study that would be required to appropriately power a multicenter trial to evaluate for noninferiority. Toward this aim number of patients eligible, reasons for ineligibility, number of eligible patients approached for the study number of patients consenting to enrollment and number of patients successfully following protocol will be reported and used, according to the table below, to design a larger trial. As patients may break randomization and go off protocol for a number of reasons (described in section 9.0 below), the proportion of patients remaining on protocol at the end of the study period will be a second key measure of feasibility.

# Eligible patients/year	% Eligible patients consented	Number of sites	Years of duration
< 15	20-30	50	2
	30-40	35	2
	40-50	28	2
15 - 25	20-30	25	2
	30-40	18	2
	40-50	15	2
>25	20-30	17	2
	30-40	12	2
	40-50	9	2
< 15	20-30	33	3
	30-40	24	3
	40-50	19	3
15 - 25	20-30	17	3
	30-40	12	3

	40-50	10	3
>25	20-30	12	3
	30-40	8	3
	40-50	7	3

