3.3.1 Primary Endpoint

The primary endpoint of this study will be feasibility of an RCT comparing a lower platelet transfusion threshold ($30 \times 10^9/L$) to a higher platelet threshold ($50 \times 10^9/L$) in patients who require anticoagulation for VTE. To assess feasibility of a multicenter RCT we will evaluate:

1. Number of patients eligible, reasons for ineligibility
2. Number of eligible patients approached for the study

3. Number of patients consenting to enrollment
4. Number of patients successfully following protocol (defined as receiving transfusions 'on protocol' at the end of the study period)

This data will then assist in determining the number of centers likely to be required to appropriately power a definitive study within 2-3 years.

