3.4 Estimated Accrual

We estimate an accrual rate of approximately one patient per month over a 12-month period. Based upon historical data we estimate approximately 25-30 patients per year will be eligible and are estimating a 45% rate of consent.

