13.2 Sample Size and Power

As this study is purely descriptive, it will not be powered to determine efficacy or safety of either intervention. The sample size has been chosen based upon the rate of enrollment necessary to establish the feasibility of an appropriately powered study.

A full trial would be a non-inferiority study powered for safety. The primary outcome would be WHO Grade 2 or above bleeding and the study would be powered to identify a relative risk of 1.4 or greater. This is based upon trials of anticoagulation, in which RR of 1.4 for bleeding is standardly considered to be acceptable.

Based on historical data, we assume a bleeding rate of $\geq 40\%$ at the higher threshold. A relative risk of 1.4 would correspond to an assumed-true bleeding rate at the lower threshold of 56% ($.56/.40 = 1.4$). If we assume that the true bleeding rate at the lower threshold is also 40% , then with 125 patients per treatment arm, we'll have approximately 84% power to deem the lower threshold non-inferior to the higher threshold (at the one-sided significance level of $.05$).

In other words, if the assumed-true bleeding rates in each arm are 40%, then the upper limit to the 95% confidence limit for the difference between the estimate bleed rates (bleed rate at lower threshold – bleed rate at higher threshold) is below 0.16 with a probability of 0.84. If we assume a true bleeding rate of 60% at the higher threshold, then a relative risk of 1.4 (or less) corresponds to an assumed-true rate in the lower threshold of 84% (or less). If the assumed-true bleeding rates in both arms is 60%, then 125 patients/arm yield approximately 99% power to deem the lower threshold as non-inferior (as defined above).

Anticipating a two-year enrollment period across fifteen sites, expecting that other sites will enroll at a slightly lower rate than the primary site randomization of 12 patients in a one-year period at our Center will be a rough benchmark for feasibility (although other factors will be considered when judging this approach as feasible for purposes of designing the randomized Phase III trial, including compliance with the study protocol and event rate).

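### At the protocol's own accrual estimate, the Section 8.1 table gives 9 sites for a 2-year trial, which yields about 211 to 243 patients rather than 250, and the 15 sites of Section 13.2 are not linked to it

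*Combined protocol and SAP*

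**What the plan says.** Section 8.1 (Primary Endpoint) states that "the primary goal is to determine the number of centers and duration of study" needed for a multicentre non-inferiority trial. It lists the pilot counts to be collected and ends the list with "number of patients successfully following protocol will be reported and used, according to the table below, to design a larger trial". The table is indexed by eligible patients per year (under 15, 15 to 25, over 25), consent (20-30, 30-40, 40-50%) and duration (2 or 3 years). It gives no formula, target total or assumption about other sites. The next sentence says "the proportion of patients remaining on protocol at the end of the study period will be a second key measure of feasibility". Section 3.3.1 says the data will "assist in determining the number of centers likely to be required to appropriately power a definitive study within 2-3 years".

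Three other statements bear on the table:

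- Section 3.4 expects that about "25-30 patients per year will be eligible and are estimating a 45% rate of consent".
- Section 13.2 (Sample Size and Power) sizes the full trial at "125 patients per treatment arm".
- The same section plans the full trial as follows: "Anticipating a two-year enrollment period across fifteen sites, expecting that other sites will enroll at a slightly lower rate than the primary site"; and "randomization of 12 patients in a one-year period at our Center will be a rough benchmark for feasibility".

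**The concern.** The table is the stated route from the pilot's result to its stated primary goal, so the cell that matters most is the one where the protocol expects to land. Except at exactly 25 eligible patients, the Section 3.4 estimate falls in the row for over 25 eligible and 40-50% consent, which gives 9 sites for 2 years. That looked too few for 250 patients even if every site matched this one, and Section 13.2 expects the others to be slower. Section 13.2 also names 15 sites for the same 2 years, with nothing to connect the two figures. A pilot that met its target exactly could then be read as supporting a 9-site, 2-year trial that would fall short of its sample size.

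**Working it through.** **Inputs.** Target 2 × 125 = 250 (Section 13.2; the table itself states no target). Eligible 25 to 30 per year and 45% consent (Section 3.4). Benchmark 12 per year (Section 13.2). Sites and years as printed in Section 8.1.

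**Reproducing the table.** The formula below is inferred: sites = 250 / (eligible × consent × years), with consent at the band midpoints and 10, 20 or 30 eligible. Each cell shows calculated → printed.

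| Eligible, years | 25% | 35% | 45% |
|---|---|---|---|
| 10, 2 | 50.0 → 50 | 35.7 → 35 | 27.8 → 28 |
| 20, 2 | 25.0 → 25 | 17.9 → 18 | 13.9 → 15 |
| 30, 2 | 16.7 → 17 | 11.9 → 12 | 9.26 → 9 |
| 10, 3 | 33.3 → 33 | 23.8 → 24 | 18.5 → 19 |
| 20, 3 | 16.7 → 17 | 11.9 → 12 | 9.26 → 10 |
| 30, 3 | 11.1 → 12 | 7.94 → 8 | 6.17 → 7 |

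Fourteen of the 18 cells yield 243 to 256.5 patients at their own midpoints, within 3% of 250, so the formula is very probably the one used. It contains no factor for slower sites. No single rounding rule fits: nearest-integer rounding matches 13 cells and rounding up matches 14. The value 9.26 is printed once as 9 and once as 10. Three cells fall short (245, 243 and 247.5) and four overshoot (270, 270, 270 and 283.5).

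**Yield of the 9-site, 2-year cell if every site matches this one.** Yield = 9 × 2 × rate. Power = Φ(0.16/√(2 × 0.4 × 0.6/n) − 1.645), with n = total/2 and the margin and 40% rates of Section 13.2. At 250 this gives 82.6%; the protocol states about 84%. The last column is the rate the other eight sites need, relative to this one: (250/(2 × rate) − 1)/8.

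| Rate here, per year | Yield | Below 250 | Power | Sites needed | Other 8 sites must run at |
|---|---|---|---|---|---|
| 26 × 0.45 = 11.7 | 210.6 | 16% | 76.6% | 10.68, so 11 | 121% |
| 12 (benchmark) | 216 | 14% | 77.5% | 10.42, so 11 | 118% |
| 30 × 0.45 = 13.5 | 243 | 3% | 81.6% | 9.26, so 10 | 103% |

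Reaching 250 needs 250/18 = 13.9 patients per site per year, or 13.9/0.45 = 30.9 eligible, above the top of the Section 3.4 range. At 12 per year, nine sites take 250/(9 × 12) = 2.31 years, or 27.8 months.

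**The 15 sites.** With 12 per year here, 15 sites reach 250 in 2 years if the other 14 run at (250/24 − 1)/14 = 67% of this site's rate. So 15 leaves room for slower sites and 9 leaves none. In the table, 15 sites for 2 years appears only in the 15-25 eligible, 40-50% cell.

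**Bin edges.** At 45% consent, going from 25 to 26 eligible moves the printed answer from 15 sites (15 × 2 × 11.25 = 337.5 patients) to 9 (210.6). The calculated need moves only from 11.1, so 12, to 10.68, so 11. Twelve randomised per year reads as 9 sites if 26 were eligible, 15 if 25 were, and 12 if 31 were (31 is outside the Section 3.4 range); 11 are needed in each case. Consent of exactly 30% or 40% falls in two rows.

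**Three years.** The 7-site entry gives 7 × 3 × 12 = 252, adequate at the benchmark if all sites are equal.

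**The case against.** The arithmetic is not in dispute; its weight is.

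- *The target and formula are inferred.* True. But 125 per arm is the only full-trial size in the document, and the match across the table is close.
- *The cell is a band, and the shortfall is specific to 45% consent.* At 28 eligible and 50% consent, nine sites give 252. At 30 and 50% they give 270, and the other eight could run at about 92% of this site's rate. This stands as a limit on the claim, but 45% is the protocol's own estimate and the cell should work there.
- *At 30 eligible the error is only 9.26 rounded down*, costing 7 patients and about one point of power. Correct; the material gap lies at the lower and middle part of the range and at the 12-per-year benchmark.
- *Slower sites are provided for in Section 13.2, and no section plans a 9-site trial.* Fair, and 15 sites would be enough under a wide range of slower rates. It leaves two unconnected answers to the question the pilot is meant to settle.
- *The table is a rough guide.* Section 3.3.1 speaks of assisting the decision, and Section 13.2 calls 12 per year rough and says other factors will be considered. Section 8.1, however, says the counts will be used according to the table.
- *Twelve patients fix the rate too loosely for this to matter.* The exact Poisson 95% interval for 12 in a year is 6.2 to 21.0, or about 21 down to 6 equal sites for 2 years. That uncertainty exceeds the rounding errors. It is a reason to report the interval, not to keep a central figure that is too low.

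The slips at 35 and 33 sites are trivial, and the overshoots are conservative.

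**Conclusion.** The point holds and should be fixed. At 26 to 30 eligible patients and 45% consent, the printed 9 sites for 2 years yield 211 to 243 patients against 250, and 216 at the 12-per-year benchmark. The calculated need is 10 or 11 sites even if all match this one, and more if the others are slower, as Section 13.2 expects. The 9 and the 15 sites are not reconciled. This rests on the inferred target of 250 and on consent near 45%. The consequence is confined to planning the full trial: a projected power of about 77% to 82% rather than 83%, or a longer enrolment period. The pilot's patients, endpoints and analyses are unaffected. A smaller point is that Section 8.1 lists the number following protocol among the quantities used through the table, which has no such input.

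**What to change.** State the target of 250 in Section 8.1 and replace the look-up with a calculation from the observed randomisations per year at this site, always rounded up. Keep reporting eligible patients and consent. Apply a declared rate ratio d to the other sites only:

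sites = 1 + (250/(years × rate here) − 1)/d

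The documents give no value for d. Assumed values at 12 per year give:

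| d | 2 years | 3 years |
|---|---|---|
| 0.9 | 11.46, so 12 | 7.60, so 8 |
| 0.8 | 12.77, so 13 | 8.43, so 9 |
| 0.7 | 14.45, so 15 | 9.49, so 10 |

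Derive the 15 sites in Section 13.2 from the same formula; at 12 per year they need d of at least 0.67. Report the projected number of sites with the interval for the accrual rate. Reword the Section 8.1 sentence so that the number following protocol is the separate compliance measure.

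The cost is one table and two sentences, with no patients or data. The only downside is a larger projected number of sites at the expected result.

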13.2 Primary/Secondary Endpoints/Hypotheses and Analytical Methods

The primary endpoints of this study are (1) enrollment and (2) compliance. Enrollment will be described at the end of a 12-month period and (2) compliance will be evaluated as described in section 3.3.1. The secondary endpoints described in sections 3.3.2 will also be reported and analyzed with descriptive statistics only. This trial is not powered to detect statistically significant differences between the study arms for these clinically important endpoints. Rather, the primary goal is to establish feasibility for enrollment into a formal trial.

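### The Section 8.1 site table gives 9, 12 or 15 sites, or no entry, for the same yearly accrual of 12, and no interval is planned (minor)

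*Combined protocol and SAP*

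**What the plan says.** Section 8.1 Primary Endpoint sets the determination of centres and duration as the pilot's main goal. The numbers eligible, approached, consenting and following protocol are to be reported and "used, according to the table below, to design a larger trial". The table is entered by "Eligible patients/year" (below 15, 15-25, above 25) and by the percentage of "Eligible patients consented" (20-30, 30-40, 40-50), for two or three years. It has no entry below 20% or above 50%.

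Section 3.3.1 is softer: "This data will then assist in determining the number of centers likely to be required to appropriately power a definitive study within 2-3 years".

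The planning values are in Section 3.4: "Based upon historical data we estimate approximately 25-30 patients per year will be eligible", and the investigators "are estimating a 45% rate of consent".

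The section on endpoints and analytical methods (the first 13.2) says "Enrollment will be described at the end of a 12-month period". It plans no interval. The sample size section (the second 13.2) says that "with 125 patients per treatment arm, we'll have approximately 84% power". It anticipates fifteen sites over two years, expects other sites to enrol somewhat more slowly, and treats 12 patients in a year as a rough benchmark.

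**The concern.** The number of sites for a fixed total depends on one quantity, patients randomized per site per year. The table splits this into two factors and bands each one. Two pilots with identical accrual can therefore be sent to different site numbers, and one that meets its enrolment target can fall off the table. The planning values sit close to an eligibility edge (25-30 against 25) and a consent edge (45% against 50%), so a difference of one or two patients can change the answer. With about 27 eligible and 12 consenting, both inputs are also imprecise, and the plan has no measure of that. At stake is a site number reported without its error and partly set by where the band edges fall. Patients in the pilot are not affected.

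**Working it through.** **Inputs.** Full trial: 125 per arm, 250 in total (13.2 Sample Size and Power). Eligible per year: 25-30, midpoint 27.5; consent 45% (Section 3.4). Pilot duration: 12 months (13.2 Primary/Secondary Endpoints). Bands and site numbers: Section 8.1. The distribution of the yearly eligible count is not in the documents. I assume Poisson and show the alternatives.

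**Reproducing the table.** Take sites = 250/(eligible per year x consent x years), with row values 10, 20 and 30 and consent midpoints 0.25, 0.35 and 0.45. The row values are inferred, not stated. All 18 cells agree within 1.2 sites:
- above 25 eligible, 40-50%, two years: 250/(30 x 0.45 x 2) = 9.3, printed 9
- 15-25 eligible, 40-50%, two years: 250/(20 x 0.45 x 2) = 13.9, printed 15 (the largest gap)

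The table is thus the direct formula evaluated at band midpoints.

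**Same accrual, different answers.** This step needs no distributional assumption. Hold the number randomized at 12 in the year:

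| Eligible | Consent | Two-year table | 250/(2 x 12) |
|---|---|---|---|
| 31 | 39% | 12 sites | 10.4 |
| 26 | 46% | 9 sites | 10.4 |
| 25 | 48% | 15 sites | 10.4 |
| 23 | 52% | no entry | 10.4 |

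From 25 to 26 eligible, one more patient is screened and does not consent, and the answer drops from 15 sites to 9. The row value jumps from 20 to 30 while the consent band stays the same.

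**How often this happens.** Let the eligible count be Poisson and consent binomial at 45%, with exactly 40% and exactly 50% counted inside the 40-50 band. The cell matching Section 3.4 is above 25 eligible with 40-50% consent (9 sites). By exact enumeration:

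| Mean eligible | Matching cell | No entry |
|---|---|---|
| 25 | 20.3% | 28% |
| 27.5 | 29.3% | 27.1% |
| 30 | 37.0% | 26.4% |

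At 27.5, the no-entry share is 26.7 points above 50% consent and 0.4 points below 20%. The other two-year readings are 12 sites 15.1%, 15 sites 14.9%, 18 sites 8.1%, 17 sites 2.8%, 25 sites 2.4%, and a below-15 row 0.2%.

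Sensitivity:
- Eligible count fixed at 26-30 rather than random: matching cell about 42-54%, no entry about 23-30%. At exactly 25 the above-25 row is never reached.
- Exactly 50% treated as off the table (mean 27.5): 25.1% and 33.8%.
- Enrolment stopped at 12, eligible count annualised (mean 27.5): about 28% and 31%.

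**Direction of error.** Under the planning values the direct need is 250/(2 x 27.5 x 0.45) = 10.1 sites. Nine is the smallest two-year entry, so every other printed two-year cell is larger than needed.

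**Precision.**
- Consent 12/27 = 44%: exact 95% interval 25-65%, which touches every consent band and runs past the table.
- 27 eligible: exact Poisson 95% interval 17.8-39.3, which spans two rows.
- 12 randomized in one year: exact Poisson 95% interval 6.20-20.96. Sites for two years: 250/(2 x 12) = 10.4, from 250/(2 x 20.96) = 6.0 to 250/(2 x 6.20) = 20.2.

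**The case against.** The strongest reply is that the table is a guide, not a rule. Section 3.3.1 says only that the data will help to determine the number of centres. The sample size section calls 12 patients a rough benchmark with other factors considered, and all raw counts will be reported, so a later designer can compute an interval. This stands, and it is the main reason the point is minor. However, the other factors named there are compliance and event rate, which do not address error in accrual, and Section 8.1 still names the table as the route.

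Second, a missing entry is not a lost answer. Nearly all such pilots have consent above 50%, and the table's own formula extends easily: at a 55% midpoint, 250/(30 x 0.55 x 2) = 7.6 and 250/(20 x 0.55 x 2) = 11.4 sites. With that extension, and mean 27.5, about 71% of pilots land at 8-12 sites (9 sites 29%, 12 sites 15%, the two extended cells 16% and 10%, before rounding), against a need of 10.1. This also stands. The plan does not specify the extension, though, and the case is too frequent to leave undefined.

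Third, the sample size section already ties fifteen sites over two years to 12 randomized in a year, so the direct measure is partly in use and the plan has some margin. That is correct. But the table cell for the same planning values says 9, and nothing in Section 8.1 links 9 to fifteen.

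Fourth, eligibility and consent are worth reporting separately because other centres may differ in each, and one centre's Poisson interval ignores differences between sites. Both are fair. The first is a reason to keep the table as illustration, the second to state the between-site allowance separately.

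**Conclusion.** The concern holds as a minor point. The table returns inconsistent site numbers for identical accrual, lacks a band that the planning values make likely to be needed, and comes with no interval. The inconsistency rests on the printed table and the 250-patient total alone. The frequencies rest on my Poisson assumption: about 20-37% of pilots in the matching cell for means of 25-30 (29% at 27.5), or about 42-54% if eligibility is fixed at 26-30, and about 26-28% with no entry under the Poisson assumption.

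Three stronger readings are not supported:
- A reader might take 29% as what follows if the protocol's assumptions are exactly true. Section 3.4 gives only an approximate range and no distribution, so the range must be quoted.
- A reader might infer that the full trial would be under-sized and run out of time or sites. In this scenario the lowest printed two-year cell is 9 against a need of 10.1, so the largest under-read from a printed cell is about one site, and the other cells over-state. Under-sizing would need other true rates, which are not examined here.
- A reader might infer that the pilot's design answer depends on the table alone. Section 3.3.1 and the sample size section do not say that.

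**What to change.** In Section 8.1 and in both parts of 13.2:

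1. Estimate sites as 250/(years x patients randomized per year) and report it with an exact interval. For 12 in one year and a two-year trial this is 10.4 sites, 95% interval 6.0-20.2. If enrolment stops at 12, base the interval on the time taken to reach 12.
2. Keep the table as an illustration, and add bands below 20% and above 50% consent.
3. State separately the allowance for slower enrolment elsewhere that leads to fifteen sites. Fifteen sites over two years implies 250/(15 x 2) = 8.3 patients per site per year, against 12 at the primary site.

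A planning limit is optional. For example, the one-sided 80% lower limit for 12 in a year is 9.03, giving 250/(2 x 9.03) = 13.8, so 14 sites. That is one fewer than the fifteen already anticipated. It covers sampling error at one centre only, not differences between sites.

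The cost is a few lines of text, with no new data and no change to conduct or sample size. The downside is that the reported site number carries a visibly wide interval.
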